## 11.4 Reporting Requirements for Adverse Events

### 11.4.1 Expedited Reporting

[figure not shown]
- The Principal Investigator must be notified within 24 hours of learning of any serious adverse events, regardless of attribution, occurring during the study.
- The UAMS IRB must be notified within 10 business days of “any unanticipated problems involving risk to subjects or others” (UPR/UPIRTSO; See UAMS IRB Policy 10.2).

### 11.4.2 Routine Reporting

All other adverse events, such as those that are expected, or are unlikely or definitely not related to the study participation, are to be reported annually as part of regular IRB continuing review.

## 12.0 STATISTICAL CONSIDERATIONS

### 12.1 Study Design/Study Endpoints

- This is a dose-escalation study with three radiation doses: 10Gy, 15Gy, and 20Gy. It uses the traditional “3+3” design to determine whether to escalate or de-escalate doses, and thereby to determine the maximum tolerated dose (MTD) on this protocol. The initial cohort of subjects will receive a 15Gy dose of GRID therapy, as shown in the diagram. The second cohort of subjects will receive either 20Gy or 10Gy of GRID, also as shown in the diagram.
- The study endpoint is dose-limiting toxicity (DLT), which is defined as a treatment-related AE of Grade 3 or higher. Subjects will be assessed at both their 30-day post-surgery visit and their 90-day post-surgery visit for presence of a DLT.

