## 2.0 STUDY SCHEMA

## 3.0 STUDY SUMMARY

Title	Phase I clinical trial of GRID therapy in pediatric osteosarcoma of the extremity
Protocol Number	205993
Phase	1
Methodology	Prospective, single-arm “3+3” dose-escalation design
Study Duration	12 months
Study Center(s)	Single center (UAMS)
Objectives	To evaluate the toxicity profile of GRID therapy using dose levels of 10Gy, 15Gy and 20Gy in pediatric osteosarcoma of the extremity.
Number of Subjects Treated	A minimum of 6 and maximum of 12 subjects will be treated.
Diagnosis and Main Inclusion Criteria	Subjects, 5-21 years of age, with a diagnosis of non-metastatic extremity osteosarcoma who have been prescribed GRID radiotherapy by their treating physician
Primary Outcome Measures	Dose-limiting toxicity (DLT), which is defined as a treatment-related AE of Grade 3 or higher, as assessed at either 30 days or 90 days following surgery.
Statistical Methodology	Rule-based evaluation of DLTs to determine the MTD of GRID

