## 5.0 STUDY OBJECTIVES

### 5.1 Primary Objectives

- 1) **Safety** - To evaluate the toxicity profile of GRID therapy using dose levels of 10Gy, 15Gy and 20Gy in pediatric osteosarcoma of the extremity.

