### 8.2 Study Assessments:

#### 8.2.1 Chemotherapy:

- Subject will receive routine chemotherapy for osteosarcoma (unless subject has already received chemotherapy)

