**8.2.3 Surgery:**

- Routine surgery for osteosarcoma

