## 11.3 Definitions

### 11.3.1 Definition of Adverse Event

An adverse event is any untoward medical occurrence in a patient undergoing study assessments and which does not necessarily have a causal relationship with the assessments. An AE can therefore be any unfavorable and unintended sign (including an abnormal laboratory finding), symptom, or disease temporally associated with the study assessments, whether or not related to the assessments.

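### The DLT must be treatment-related, but its only scheduled assessments come after surgery, with no graded AE record before GRID or between GRID and surgery

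*Combined protocol and SAP*

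**What the plan says.** **Endpoint.** Section 12.1 sets the single criterion: "dose-limiting toxicity (DLT), which is defined as a treatment-related AE of Grade 3 or higher". The Study Summary (3.0) repeats it as a "treatment-related AE of Grade 3 or higher, as assessed at either 30 days or 90 days following surgery". Section 12.1 requires both visits where 3.0 says either, but both sections place the check after surgery. Neither names the treatment to which the event must be related.

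**Purpose.** Section 3.0 describes the method as "Rule-based evaluation of DLTs to determine the MTD of GRID", and the primary objective (5.1) is "To evaluate the toxicity profile of GRID therapy using dose levels of 10Gy, 15Gy and 20Gy".

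**Sequence.** Under 7.1 each subject has chemotherapy (unless already given), then GRID, then surgery, then post-surgical chemotherapy as prescribed.

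**Schedule.** Section 8.1 asks for no protocol-specific baseline procedure. Section 8.2 lists chemotherapy, GRID, surgery and two post-surgery visits. AE assessment appears only at those two visits.

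**AE monitoring.** Section 11.2 follows events until a post-GRID visit and refers to a return to baseline. Section 11.4.1 requires the Principal Investigator to be told of any SAE during the study within 24 hours, whatever its cause.

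**Shared causes.** Section 11.1 includes, in its list of GRID-related risks, infection or poor healing after radiation, chemotherapy and surgery in combination.

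**The concern.** The endpoint is a causal judgement, made by counting events in cohorts of three or six with no control group. Such a judgement needs to know what was present before GRID and what appeared between GRID and the operation. The plan schedules neither observation.

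Two errors follow, in opposite directions. A GRID event that clears before surgery, or that is put down to the operation, goes uncounted and makes the dose look safer. A toxicity already present from chemotherapy, or a purely surgical complication, may be counted and make the dose look worse. Section 4.1 says that GRID toxicity in children is unknown at any dose, so there is no outside expectation to correct either error. Because the rules in 12.2 act on raw counts, a single event can matter.

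**Working it through.** **1. What is scheduled, in time order**

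- Before GRID: no AE assessment (8.1, 8.2.1). Section 11.2 nevertheless relies on a baseline.
- GRID: 8.2.2 lists no AE assessment.
- Between GRID and surgery: no visit in 8.2. The post-GRID visit of 11.2 has no counterpart there.
- Surgery: 8.2.3 lists no AE assessment.
- Days 30 and 90 after surgery, each ±7 days: physical exam and AE assessment (8.2.4, 8.2.5).
- Throughout: SAE notification (11.4.1), for serious events only. The DLT rests on CTCAE grade, and the seriousness criteria in 11.3.3 are not grade-based, so a Grade 3 event need not be an SAE.

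**2. The plan's own figure**

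Section 12.3 gives 6 to 12 subjects. The shortest path through Tables 1 to 3 is 3 + 3 = 6 and the longest is 6 + 6 = 12. This reproduces.

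**3. What one event does in Table 1 (15Gy)**

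- Sole event, counted: 1/3, expand, 1/6, next cohort 20Gy. Missed: 0/3, next cohort 20Gy. The direction is the same.
- One other DLT already counted, six subjects: 1/6 leads to 20Gy and 2/6 to 10Gy. The direction reverses.
- One other DLT already counted, three subjects: 2/3 leads to 10Gy; 1/3 expands and, with no further DLT, ends at 1/6 and 20Gy.

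After escalation only 20Gy or 15Gy can be declared the MTD. After de-escalation the only results are that 10Gy is the MTD or that 10Gy is above it. The two sets do not overlap.

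**4. Sensitivity at assumed rates (none is in the documents)**

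Let g be the rate of clear GRID DLTs, taken as 10% at every dose. Let s be the rate of Grade 3+ events that are missed or of disputed cause, independent of the first. If such events are not counted, p = g. If all are counted, p = 1 − (1 − g)(1 − s).

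- P(next cohort 20Gy) = (1 − p)³ + 3p(1 − p)⁵
- P(at most 1/6 in second cohort) = (1 − p)⁶ + 6p(1 − p)⁵
- P(20Gy declared) = product of the two

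Not counted, p = 0.10: 0.729 + 0.177 = 0.906; 0.531 + 0.354 = 0.886; product 0.803.

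Counted, s = 10%, p = 1 − 0.9 × 0.9 = 0.19: 0.531 + 0.199 = 0.730; 0.282 + 0.397 = 0.680; product 0.496.

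Counting more events can only move a trial from escalation to de-escalation, so the chance of opposite directions is the difference: 0.906 − 0.730 = 0.176. For other values of s:

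- s = 2%: p = 0.118, opposite direction 0.031, 20Gy declared 0.743
- s = 5%: p = 0.145, opposite direction 0.082, 20Gy declared 0.649
- s = 20%: p = 0.28, opposite direction 0.370, 20Gy declared 0.249

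At s = 10% the error can run either way. If the extra events are not due to GRID, counting them lowers the chance of declaring 20Gy from 0.80 to 0.50. If they are due to GRID and are missed, that chance rises from 0.50 to 0.80.

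**5. How much is due to a single event**

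Enumerating all outcomes for six potential subjects at g = 10%, exactly one missed or disputed event accounts for 9.8 of the 17.6 percentage points at s = 10% and for 12.2 of the 37.0 at s = 20%. The rest needs several. With g = 0, no reversal comes from a single event, in line with step 3.

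**The case against.** **GRID is plainly the intended cause.** Sections 3.0 and 5.1 name GRID, 11.2 speaks of a single study agent, and chemotherapy and surgery are called routine. That stands. A reader might infer a stronger point from 11.3.1, which says that an AE "does not necessarily have a causal relationship with the assessments" and counts events "whether or not related to the assessments". Since "8.2 Study Assessments" includes "Routine surgery for osteosarcoma" and chemotherapy, the plan might seem to contain a second, conflicting DLT rule that takes in surgical events. It does not. Section 11.3.1 is a cause-neutral definition of an AE and sets no attribution rule for a DLT. The term treatment-related is undefined and the surrounding terms vary, which is less than a contradiction.

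**Early events are not invisible.** SAEs are notified throughout, 13.2 has data collected at each subject visit, and routine clinical notes will exist. A post-surgery assessment may also look back. In addition, the Medical Monitor reviews safety data (13.3.1), and two SAEs attributed to the study suspend it (13.3.3). So it would be wrong to say that AEs are seen only after surgery; the statement holds for scheduled AE assessments. These provisions still do not call for a graded record before GRID or before surgery, and the plan states no look-back period. The schema in 2.0 and a figure in 11.4.1 could not be read in the text available, so a visit shown only there would narrow the point.

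**The extra recordings would not settle the hardest case.** A wound infection after surgery is absent at both earlier times, so they cannot attribute it. This is correct and limits what the fix achieves.

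**Conclusion.** The point holds as a gap in ascertaining the only endpoint that drives Tables 1 to 3. That endpoint requires a causal judgement, while its scheduled checks begin only when surgery is already a competing cause, with no graded record from before GRID or before the operation. The missing post-GRID visit is an internal inconsistency between 11.2 and 8.2.

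The consequence is conditional. One missed or misattributed event reverses the direction of the second cohort only alongside another counted DLT; alone, it does not.

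The percentages show how sensitive the 3+3 rules are to attribution. They compare counting all such events with counting none, at assumed and independent rates. Section 11.1 classes infection and poor healing as less likely, so 20% is a stress case, and at 2% the chance of reversal is about 3%. They should not be read as the cost of the wording or as the amount that the fix would recover, because shared-cause events remain a judgement after GRID is named. This is a change worth making, held with medium confidence.

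**What to change.** 1. Add a CTCAE-graded AE recording before GRID, for example at the radiation visit already in 7.1, and another before surgery. Enter both in 8.2.
2. Reconcile the post-GRID visit in 11.2 with the 8.2 schedule, and say which record is the baseline.
3. As accompanying clarifications, name GRID in both DLT sentences (3.0 and 12.1). The sponsor should also state how shared-cause events, including the infection and healing item in 11.1, are attributed for DLT counting, and by which role.

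The cost is two short recordings for each of at most 12 treated subjects (2 × 12 = 24 in all) and a few sentences of text. The decision tables and the range of 6 to 12 subjects are unchanged. The recordings help to identify GRID events before surgery and chemotherapy toxicity already present. They cannot decide the cause of a post-surgical wound infection.

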## 12.2 Evaluation Plan

- **Table 1** shows how the number of DLTs in the initial cohort will be used to determine whether to escalate or de-escalate the GRID dose in the next cohort.

Table 1: Toxicity Decision Rules for Initial Cohort (GRID at 15Gy)	
DLTs/ Cohort	Action
0/3	Begin accrual to Escalation Cohort
1/3	Expand Initial Cohort to 6 subjects
1/6	Begin accrual to Escalation Cohort
2/6, 3/6, or 4/6	Begin Accrual to De-Escalation Cohort
2/3 or 3/3	Begin Accrual to De-Escalation Cohort

 DLT = Dose-Limiting Toxicity

- If the second cohort is the Escalation cohort, then **Table 2** shows how the number of DLTs will be used to determine the MTD on this protocol.

Table 2: Toxicity Decision Rules for Escalation Cohort (GRID at 20Gy)	
DLTs/ Cohort	Action
0/3 or 1/3	Expand cohort to 6 subjects
0/6 or 1/6	Stop: Declare escalation dose to be the MTD 
2/6, 3/6, or 4/6	Stop: Previous dose level is the MTD 
2/3 or 3/3	Stop: Previous dose level is the MTD 

 DLT = Dose-Limiting Toxicity

 MTD = Maximum Tolerated Dose

- On the other hand, if the second cohort is the De-Escalation cohort, then **Table 3** shows how the number of DLTs will be used to determine whether 10Gy is at or above the MTD on this protocol.

Table 3: Toxicity Decision Rules for De-Escalation Cohort (GRID at 10Gy)	
DLTs/ Cohort	Action
0/3 or 1/3	Expand cohort to 6 subjects.
0/6 or 1/6	Stop: De-escalation dose level is the MTD 
2/6, 3/6, or 4/6	Stop: De-escalation dose level is above MTD 
2/3 or 3/3	Stop: De-escalation dose level is above MTD 

 DLT = Dose-Limiting Toxicity

 MTD = Maximum Tolerated Dose

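### Table 2 names 20Gy, the highest planned dose, as the MTD after 0/6 or 1/6 DLTs, although no higher dose is tested to show that it is the maximum

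*Combined protocol and SAP*

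**What the plan says.** Section 12.1 sets the dose range: "This is a dose-escalation study with three radiation doses: 10Gy, 15Gy, and 20Gy". It fixes the start: "The initial cohort of subjects will receive a 15Gy dose of GRID therapy, as shown in the diagram". It then limits what follows: "The second cohort of subjects will receive either 20Gy or 10Gy of GRID".

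Section 12.2 gives the decision rules. In Table 2 (20Gy), the action after 0/6 or 1/6 DLTs is "Stop: Declare escalation dose to be the MTD". With two or more DLTs at 20Gy, the previous level (15Gy) is the MTD. In Table 3 (10Gy), two or more DLTs lead to "Stop: De-escalation dose level is above MTD", and no MTD is named.

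Sections 12.1, 12.2 and 12.3 attach the qualifier *on this protocol* to the MTD. Two other places do not. The Statistical Methodology line in Section 3.0 reads "Rule-based evaluation of DLTs to determine the MTD of GRID", and Section 5.2 speaks of the MTD, and/or a recommended Phase 2 dose, of GRID in this population.

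The primary objective in Section 5.1 is "To evaluate the toxicity profile of GRID therapy using dose levels of 10Gy, 15Gy and 20Gy in pediatric osteosarcoma of the extremity".

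**The concern.** A dose is shown to be the maximum tolerated when it is tolerated and a higher one is not. At 20Gy the second half is missing, because the design has no higher level. The Table 2 row therefore states more than the data from that cohort can support. It would do so even if GRID caused no DLT at any dose.

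Determining the MTD is a stated objective, and the value reported is what later work would carry forward. A report that calls 20Gy the MTD does not distinguish a limit that was found from a range that ran out.

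**Working it through.** **Inputs.** Doses, starting dose and second cohort are from Section 12.1; decision rules are from Tables 1 to 3 in Section 12.2. The true DLT rates are assumptions, since the documents give none. Write p for the rate at 15Gy and q for the rate at 20Gy, with subjects treated as independent.

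**The plan's own figure.** Section 12.3 states 6 to 12 subjects. The shortest path is 3 + 3 = 6 and the longest is 6 + 6 = 12, so the range is reproduced. Naming 20Gy the MTD takes six subjects at 20Gy after three or six at 15Gy, which is 9 or 12.

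**What supports each possible conclusion**

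| Conclusion | Dose that met the 0/6 or 1/6 rule, or passed Table 1 | Higher dose that failed |
|---|---|---|
| MTD is 20Gy | 20Gy | none tested |
| MTD is 15Gy | 15Gy | 20Gy |
| MTD is 10Gy | 10Gy | 15Gy |
| 10Gy is above the MTD | none | no MTD named |

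Only the first row names an MTD with no failure above it.

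**How often that ending occurs**

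15Gy passes Table 1 with 0/3, or with 1/3 followed by 0/3:

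A = (1−p)³ + 3p(1−p)² × (1−p)³ = (1−p)³ + 3p(1−p)⁵

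20Gy passes Table 2 with 0/6 or 1/6 in total (0/3 then 0/3 or 1/3, or 1/3 then 0/3):

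B = (1−q)⁶ + 6q(1−q)⁵

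P(20Gy declared the MTD) = A × B. The share of those declarations made with 0/6 is (1−q)⁶ / B. The 10Gy rate does not enter.

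| Assumed rates 10/15/20Gy | A | B | A × B | Share with 0/6 |
|---|---|---|---|---|
| 0/0/0% | 1.000 | 1.000 | 100% | 100% |
| 5/5/10% | 0.857 + 0.116 = 0.973 | 0.531 + 0.354 = 0.886 | 86% | 60% |
| 5/10/15% | 0.729 + 0.177 = 0.906 | 0.377 + 0.399 = 0.776 | 70% | 49% |
| 5/10/20% | 0.906 | 0.262 + 0.393 = 0.655 | 59% | 40% |
| 10/20/33% | 0.512 + 0.197 = 0.709 | 0.090 + 0.267 = 0.358 | 25% | 25% |

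**What the 20Gy cohort can say.** The exact one-sided 95% upper bound on the DLT rate at 20Gy is 39.3% after 0/6 (1 − 0.05^(1/6)) and 58.2% after 1/6. Both describe 20Gy itself. Neither carries information about a higher dose.

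**Dose levels treated.** Table 1 leads to 20Gy or to 10Gy, and every path through Table 2 or Table 3 then ends in a stop. Each completed path therefore treats 15Gy and one other dose. This needs no assumed rates.

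**The case against.** The strongest defence is that the term is already limited. Sections 12.1 to 12.3 repeat the qualifier *on this protocol*, and Section 12.3 lists 10, 15 and 20Gy as the values the MTD may take. Read together, they suggest that MTD means the highest planned dose that meets the rule. Section 5.2 also allows a recommended Phase 2 dose in place of an MTD. This is a fair reading and it softens the point. It does not remove it: the phrase is nowhere defined that way, it is absent from the Table 2 row itself, and Sections 3.0 and 5.2 drop it.

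The contrast with Table 3 is not proof of an error. When 10Gy fails, no planned dose is tolerable, so none can be named; when 20Gy passes, one can. The contrast shows only that the tables provide for an open result at the lower end and not at the upper.

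Three stronger readings are tempting, and the documents do not support them:

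- *The protocol claims that doses above 20Gy are not tolerated.* No section says so. The fault is a label and a missing outcome.
- *The top-dose ending is the most likely one.* Section 4.1 hypothesises a favourable toxicity profile but also says that toxicity in children is unknown at any dose. The probability depends on the assumed rates and falls to 25% at 10/20/33%.
- *The primary objective cannot be met on any path.* That requires Section 5.1 to promise data at every level. Its wording can equally mean the set of available doses, and Section 12.1 says openly that the second cohort gets one dose or the other. An untreated planned level is also a different matter from an untested dose above 20Gy.

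**Conclusion.** The concern holds as a fault in the stated conclusion. After 0/6 or 1/6 at 20Gy, the data support the statement that the highest planned dose met the tolerability rule. They do not support the statement that it is the MTD of GRID in this population. This follows from the design alone.

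Its frequency rests on assumed DLT rates: 86%, 70%, 59% or 25% of trials across the four non-zero scenarios, and every trial if there is no toxicity. The 6 to 12 subject range, the escalation rules and their probabilities are unaffected. The primary objective needs a wording clarification and no more.

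**What to change.** Change the Table 2 action for 0/6 or 1/6 to: *Stop: MTD not reached (not exceeded); 20Gy is the highest planned dose tested and met the tolerability rule.* Align Sections 3.0, 5.2 and 12.3 so that each allows for this outcome. Table 2 should not add a dose recommendation; any recommended Phase 2 dose stays the sponsor's decision under Section 5.2.

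As a minor clarification, note in Section 5.1 and in the Section 3.0 objective that the design treats 15Gy and one of 10Gy or 20Gy, never all three.

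The cost is a less strong stated conclusion on that path. Subjects, visits and dose decisions do not change.

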## 12.3 Sample Size Estimation.

If the MTD on this protocol is 10Gy, 15Gy, or 20Gy, then the above 3+3 dose-escalation design will find it using a minimum of 6 and maximum of 12 subjects. On the other hand, if 10Gy is above the MTD on this protocol, then the above 3+3 dose-escalation design will uncover that fact using a minimum of 6 and maximum of 12 subjects. Therefore, the minimum number accrued to this protocol will be 6 subjects, while the maximum number accrued to this protocol will be 12 subjects.

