**1.0 LIST OF ABBREVIATIONS**

AE	Adverse Event
C3PR	Cancer Biomedical Informatics Grid
CCTO	Cancer Clinical Trials Office
Co-PI	Co-Investigator
CRA	Clinical Research Assistant
CRF	Case Report Form
CTCAE	Common Terminology Criteria for Adverse Events
DLT	Dose Limiting Toxicity
FDA	Federal Drug Administration
Gy	Gray
GCP	Good Clinical Practice
GRID	Spatially Fractionated Radiation Therapy
IRB	Institutional Review Board
MTD	Maximum Tolerated Dose
NCI	National Cancer Institute
ORRA	Office of Research Regulatory Affairs
PI	Principal Investigator
SAE	Serious Adverse Event
SOP	Standard Operating Procedure
UAMS	University of Arkansas for Medical Sciences

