Spatially fractionated radiotherapy (GRID) is a technique of irradiation that has been used successfully for the curative or palliative treatment of bulky tumors  $\geq 6$  cm [5-7]. Irradiation is delivered through a specially made grid collimator or by using a multi-leaf collimator (MLC) as a grid field shaper [5, 8-10]. In GRID therapy the target volume does not receive a homogeneous dose of radiation. Only the volume under the open grid areas receives irradiation from the primary beam. Our results [11] have shown that GRID followed by definitive chemoradiation resulted in excellent control of bulky disease (79%) in patients with locally advanced squamous-cell carcinoma of the head and neck. In these patients, acute toxicity profiles were acceptable and were similar to reports of chemotherapy and radiotherapy alone. In addition, no patient has developed a local recurrence in the irradiated GRID volume, but several have developed distant metastatic disease, which is common in this population. Our series also demonstrated that GRID is a feasible and valuable therapeutic option for bulky disease presentation. The therapeutic advantage of GRID therapy has been evaluated. Zwicker [12] et al reported that, for a wide range of tumor radiosensitivities, GRID therapy may have a significant therapeutic advantage over open-field radiotherapy to achieve the same level of tumor-cell kill. Highly radioresistant,

hypoxic cells are often present in bulky untreated tumors, and it is in these cases in which GRID use appears more advantageous.

Based on the above clinical experience, we hypothesize that GRID can be used safely in pediatric patients with osteosarcoma of the extremity, and will show a favorable toxicity profile in this population. However, the toxicity profile of GRID therapy, at any dose level, in pediatric patients is unknown.

Therefore, the purpose of this phase 1 clinical trial is to investigate the toxicity profile of GRID in pediatric osteosarcoma of the extremity.

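### Does section 12.3 promise to find the MTD with a certainty that a 3+3 design cannot give, so that the sample size text must change?

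*Combined protocol and SAP*

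**What the plan says.** Section 12.3 is the whole of the sample size argument. It first supposes that the MTD is one of the three doses and states "then the above 3+3 dose-escalation design will find it using a minimum of 6 and maximum of 12 subjects". It then supposes that 10Gy is above the MTD and states "then the above 3+3 dose-escalation design will uncover that fact using a minimum of 6 and maximum of 12 subjects". It concludes that accrual will be at least 6 and at most 12. It gives no DLT rate and no probability.

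The rules are in section 12.2:

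- **Table 1 (15Gy, first cohort).** 0/3 or 1/6 leads to "Begin accrual to Escalation Cohort". 1/3 expands the cohort to six. Any other result sends the trial to 10Gy.
- **Table 2 (20Gy).** 0/3 or 1/3 expands to six, and at most 1/6 makes 20Gy the MTD. Otherwise: "Stop: Previous dose level is the MTD".
- **Table 3 (10Gy).** Same thresholds. At most 1/6 makes 10Gy the MTD. Otherwise: "Stop: De-escalation dose level is above MTD".

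Section 12.1 says the 3+3 is used to decide on escalation or de-escalation and "thereby to determine the maximum tolerated dose (MTD) on this protocol". The list of abbreviations expands the term to "Maximum Tolerated Dose" and does not tie it to a DLT rate. Nor does any other section.

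**The concern.** The conditional form of 12.3 treats the MTD as a fact that exists before the trial and that the trial is bound to discover. Cohorts of three or six cannot do that. Whatever happens at the other doses, a dose cannot be named more often than it passes its own rule, and that chance falls quickly as the DLT rate rises.

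The point matters because 12.3 is the only justification of sample size, and because section 5.2 makes the MTD and/or recommended Phase 2 dose a secondary objective. The second statement in 12.3 bears on safety. Section 4.1 says that "the toxicity profile of GRID therapy, at any dose level, in pediatric patients is unknown", and a reader could take 12.3 as assurance that the trial will show it if even the lowest dose is too toxic. The natural request would be to replace the two statements with a table of operating characteristics and a stated tolerable DLT rate.

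**Working it through.** **Inputs.** The cohort rules come from Tables 1-3 in section 12.2, the starting dose of 15Gy from section 12.1. The DLT rates are assumptions, because the documents give none. Subjects are treated as independent and all evaluable. The two-SAE suspension in section 13.3.3 is not modelled.

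**Step 1: the plan's own figure.** The first cohort ends at 3 subjects (0, 2 or 3 DLTs) or 6 (after 1/3). The second ends at 3 (2/3 or 3/3) or 6 (after 0/3 or 1/3). The possible totals are 3+3 = 6, 3+6 = 9, 6+3 = 9 and 6+6 = 12, so 6 to 12 is reproduced. By outcome:

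| Outcome | Possible N |
|---|---|
| 15Gy named | 6, 9 or 12 |
| 20Gy named | 9 or 12 |
| 10Gy named | 9 or 12 |
| 10Gy above MTD | 6, 9 or 12 |

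Naming 10Gy or 20Gy needs a full six at that dose, hence at least 9 in all. The overall minimum of 6 still holds. For example, 2/3 at 15Gy followed by 2/3 at 10Gy ends at 6.

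**Step 2: chance that a dose passes its own rule.**

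- 15Gy: C1(p) = (1-p)^3 + 3p(1-p)^2 × (1-p)^3 = (1-p)^3 + 3p(1-p)^5
- 10Gy or 20Gy: C2(p) = P(at most 1 DLT in 6) = (1-p)^6 + 6p(1-p)^5

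At p = 0.20:

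- C1 = 0.512 + 0.6 × 0.32768 = 0.7086
- C2 = 0.262144 + 1.2 × 0.32768 = 0.6554

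**Step 3: outcome probabilities.**

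- P(name 15Gy) = C1(p15) × (1 - C2(p20)), at most C1(p15)
- P(name 20Gy) = C1(p15) × C2(p20), at most C2(p20)
- P(name 10Gy) = (1 - C1(p15)) × C2(p10), at most C2(p10)
- P(10Gy above MTD) = (1 - C1(p15)) × (1 - C2(p10))

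The ceilings are reached only if the other dose has a DLT rate of 0% or 100%, whichever helps:

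| True DLT rate at the dose | Ceiling, 15Gy | Ceiling, 10Gy or 20Gy |
|---|---|---|
| 5% | 97.3% | 96.7% |
| 10% | 90.6% | 88.6% |
| 20% | 70.9% | 65.5% |
| 30% | 49.4% | 42.0% |
| one third | 42.8% | 35.1% |

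**Step 4: full scenarios (assumed rates at 10/15/20Gy).**

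| Rates | 10Gy named | 15Gy named | 20Gy named | 10Gy above MTD |
|---|---|---|---|---|
| 5/5/5% | – | – | 94.2% | – |
| 5/10/20% | 9.1% | 31.2% | 59.4% | 0.3% |
| 20/40/60% | 45.3% | 29.7% | 1.3% | 23.8% |
| 40/50/60% | 19.3% | 16.5% | 0.7% | 63.5% |

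In the first row only the 20Gy outcome is needed here: 0.9734 × 0.9672 = 0.942. In the last row, P(10Gy above MTD) = (1 - 0.1719) × (1 - 0.2333) = 0.635, so some dose is still named in 36.5% of trials. Of that, 19.3 + 16.5 = 35.8 points come from paths with at least two DLTs, because 10Gy is named only after 15Gy fails and 15Gy only after 20Gy fails.

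**Step 5: what 12.3 claims.** Sections 12.1, 12.2 and 12.3 all use the qualified phrase MTD on this protocol, and the study summary calls the method rule-based. On that usage the MTD is the output of the tables, and 12.3 says that every path ends in one of four outcomes with 6 to 12 subjects. Step 1 shows that this is correct.

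**The case for a change.** The strongest case for a change runs as follows. The if-then form of 12.3, and its talk of uncovering a fact, read more naturally as statements about a true state of affairs. If the MTD is only what the tables return, the statements are circular and say nothing about whether 6 to 12 subjects are enough. They are also slightly inexact, since 10Gy or 20Gy cannot be named with 6. Everyone may know that a 3+3 is approximate, but then the text could say so at almost no cost. The two-SAE suspension in 13.3.3 prompts a review and names no dose, so it does not rescue the wording.

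Much of this stands. The verbs are too strong on the first reading, and no non-zero DLT rate makes them true. But in a rule-based 3+3 the sample size does follow from the cohort rules, and that derivation is the support 12.3 offers. The size of the shortfall depends on DLT rates that the documents do not give, and section 4.1 expects only minor side effects and a favourable toxicity profile. At 5-10% the ceilings are high. The figure of 36.5% needs section 13.3.3 beside it: nearly all of those paths contain two or more DLTs, and two attributable SAEs suspend the trial. A Grade 3 event need not be an SAE, so that protection is likely but not assured.

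**Conclusion.** No change is needed. Section 12.3 is worded with more confidence than a 3+3 can support, but its one quantitative conclusion, 6 to 12 subjects, is right, and it states no probability that could be wrong. At an assumed 20% DLT rate the chance of naming the true MTD dose is at most 70.9% (15Gy) or 65.5% (10Gy or 20Gy). These ceilings rest on independent, fully evaluable subjects and on the assumed rate, and they run from 97% at 5% down to 43% and 35% at one third.

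Rewording would leave the tables, the accrual range, the analysis and the dose named from any given data exactly as they are. An operating-characteristics table would rest on assumed toxicity rates in a population where the protocol says toxicity is unknown, so it would illustrate the design without correcting it. Limited precision from cohorts of three or six is the accepted price of a small rule-based phase 1 trial. The primary objective here (section 5.1) is the toxicity profile, with the MTD secondary. Anyone who takes a named dose forward should treat it as an estimate, and can compute its uncertainty from Tables 1-3 as they stand.
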